5.6.1.2. Analysis of Adverse Events

The verbatim terms used in the eCRF by investigators to identify AEs will be coded using the Medical Dictionary for Regulatory Activities.

Number and percentage of participants with at least one specific AE (solicited/unsolicited) will be tabulated. Solicited AEs will be summarized by class (local and systemic) and preferred term. Unsolicited AEs will be summarized by System Organ Class and Preferred Term.

For solicited AEs, following tables will be provided: summary, by worst severity grade, at least Grade 3, related (systemic only), time to onset (in days) and duration (in days). Note: Duration is defined as number of days from the start of the event until resolution of the event. The time to first onset is defined as (date of first onset – reference date + 1). The reference date is the start date of the vaccination period.

For unsolicited AEs, the following tables will be provided as appropriate: summary, all events, most frequent, at least Grade 3, related AE, AE leading to study vaccine discontinuation, AE leading to study discontinuation, participants who died, MAAE, related MAAE, SAE and related SAE.

Summaries, listings, datasets, or participant narratives may be provided, as appropriate, for those participants who die, who discontinue vaccination due to an AE, who discontinue study due to an AE, MAAE or who experience a severe or a SAE.

Summaries and/or listings may be provided separately for AEs with onset outside the above defined timeframe (i.e., beyond 29 days post-vaccination).

5.6.1.3. Phase Allocation of Adverse Events

Step 1: Allocation of events to the periods:

As the analysis of solicited events will be based on the overall assessment of the investigators which is documented in the CE domain, the ADaM dataset will be based on the CE domain. Solicited events are allocated to the phases as described below, however they are always allocated to the respective Post-dose period and will never be attributed to the screening phase. Time of day is not considered while attributing solicited AEs to phases.

Unsolicited adverse events are allocated to periods based on their start date/time. If the start date/time of an event falls between (or on) the start and stop date/time of a period, the AE is attributed to that period (treatment-emergent principle).

- In case of partial start or stop dates (i.e., time and/or day and/or month and/or year missing), the events are allocated to the periods using the available partial information on start and end date; no imputation will be done. If, for instance, the AE start date only month and year are available, these data are compared to the month and year information of the periods. This rule may lead to multiplication of the event as a consequence of its assignment to multiple periods.

- In case of a completely missing end date, the date is imputed by the cut-off date of the analysis for participants still ongoing in the study, and by the end date of the last period for participants who discontinued or completed the trial. In case of a completely missing start date, the event is allocated to the first active treatment phase (Post-dose 1 period), except if the end date of the AE falls before the start of the first active treatment phase (Post-dose 1 period).

Step 2: Combination of Events:

Overlapping/consecutive events are defined as events of the same participant with the same preferred term which have at least 1 day overlap or for which the start date of an event is 1 day after the end date of the preceding event. Overlapping/consecutive events may be combined into one AE or not, according to the following rules:

- 1) If overlapping/consecutive events start in one of the following phases/periods - Screening or Follow-up (defined as non-active periods) - followed by an AE in - Post-dose period (defined as active period) - they are allocated to their respective phases/periods and are considered as separate events.
- 2) In case overlapping/consecutive events start within a single period, they are considered as one and the same AE. The individual events which contribute to this AE are retained as individual records in the ADaM database but are assigned the same onset, period, and total duration. All related attributes to the AE/phase/period should also be consistent with the new event.
- 3) In case overlapping/consecutive events start in both an active period followed by a consecutive non-active period, they are allocated to the active period only and are considered as one and the same AE. The individual events which contribute to this AE are retained as individual records in the ADaM database but are assigned the same onset, treatment period, and total duration. All related attributes to the AE/phase/period should also be consistent with the new event.
- 4) In case an active period is followed by another active period, and the overlapping/consecutive events start in both periods, they are allocated to their respective period and are considered as separate AEs. In case overlapping/consecutive events start in non-consecutive periods (regardless of active or non-active), they are allocated to their respective period and are considered as separate AEs.
- 5) In case a non-active period is followed by another non-active period, and the overlapping/consecutive events start in both periods, they are allocated to the first period and they are considered as one and the same AE. The individual events which contribute to this AE are retained as individual records in the ADaM database but are assigned the same onset, period, and total duration. All related attributes to the AE/phase/period should also be consistent with the new event.

Remarks:

1. Events can only be combined into one and the same AE if their start and stop dates are known.
2. In case the completely missing end date is imputed (for period allocation), this date is also considered as a complete date.
3. Time is not considered when determining overlap of events.

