#### **Risks Related to ExPEC9V**

Based on 2 completed Phase 1 studies and 2 completed Phase 2 studies in the ExPEC4V development program, most solicited (local and systemic) AEs started on Days 1 to 3 post-vaccination. Headache and fatigue/tiredness were the most frequent solicited AEs, reported as early onset events, with a median time of onset of 2 and 3 days, respectively. Late onset solicited (mainly local) AEs were observed starting Days 6 to 8 post-vaccination. Pain/tenderness represented a majority of the late onset AEs and were Grade 1 in severity. There was a tendency for higher incidence of late onset AEs with higher ExPEC4V doses.

Late onset solicited AEs were also observed in ExPEC10V development program. The median time to first onset of local solicited AEs was 2 to 2.5 days after vaccination for those in the ExPEC10V dose groups. The most frequent solicited AEs, pain/tenderness, fatigue, myalgia, and headache occurred mostly as early onset events. Injection site erythema and swelling occurred as late onset events (time to first onset >5 days after vaccination) in the majority of participants from the combined ExPEC10V groups. In the combined ExPEC10V groups, 8 (2.6%) participants experienced late onset AEs with Grade 3 severity. A trend towards increased local reactogenicity with higher doses of ExPEC10V was observed.

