## **6. STUDY VACCINATIONS AND CONCOMITANT THERAPY**

### **6.1. Study Vaccinations Administered**

Participants will be vaccinated according to the schedule detailed in the [Schedule of Activities \(SoA\)](#). For description of the vaccinations, see below.

On Day 1, each participant will receive 2 IM injections, 1 in each arm; on Day 30, each participant will receive 1 IM injection. The right arm should be used for seasonal influenza vaccination on Day 1; the left arm should be used for ExPEC9V or placebo vaccination on Days 1 and 30. Two injections in the same deltoid are allowed only if medically indicated. If an injection cannot be given in the deltoids due to a medical condition or other contraindication (for example, due to the extent of tattoos which are felt to interfere with the examination of the injection site), use alternative locations such as the hip, thigh or buttocks (to be avoided in overweight participants). In all circumstances, IM injections in other locations than the upper arm are not considered protocol deviations.

For information on vaccination windows, see Section 8., Study Assessments and Procedures. If a participant cannot be vaccinated within the allowed window, the decision regarding vaccination will be assessed on a case-by-case basis, upon discussion between sponsor and investigator.

Study vaccination administration must be captured in the source documents and the eCRF.

VAC52416 (JNJ-78901563) will be manufactured and provided under the responsibility of the sponsor. Refer to the IB for a list of excipients.

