5.6. Safety Analyses

Safety data will be summarized descriptively. No formal statistical testing of safety data is planned. If analysis by age group and by history of UTI is performed, stratification factor data are obtained as collected from the eCRF.

Safety endpoints (secondary endpoints):

- Solicited local (in each injection site for the first vaccination) and systemic AEs for 14 days post each vaccination
- Unsolicited AEs for 29 days post each vaccination
- MAAEs and SAEs collected from the administration of first vaccination until 6 months post last vaccination

Safety analyses will be performed on the FAS. Continuous variables will be summarized using the following statistics, as appropriate: number of observations, mean, 95% CI for the mean, median, quartiles (1st and 3rd), minimum, and maximum. Frequencies and percentages (one decimal place) will be generated for categorical variables. No formal comparisons between groups will be provided.

Safety data will be analyzed and presented by study intervention and phase, and across the entire study period where applicable. For solicited AEs, the denominator for the percentages is the number of participants with data assessed by the investigator in the considered population and phase for a certain regimen (incidence per 100 participants/phase). For unsolicited AE, the denominator for the percentages is the number of participants in the considered population and phase for a certain regimen (incidence per 100 participants/phase).

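### The adverse-event merge rule in SAP 5.6.1.3 has no injection-site key, so onset and duration of Day 1 local reactions can be pooled across the two injection sites

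*SAP*

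**What the plan says.** Protocol 6.1 sets out the injections: "On Day 1, each participant will receive 2 IM injections, 1 in each arm; on Day 30, each participant will receive 1 IM injection". Influenza vaccine goes in the right arm, and ExPEC9V or placebo in the left. SAP 5.6 accordingly makes the local endpoint site-specific: "Solicited local (in each injection site for the first vaccination) and systemic AEs for 14 days post each vaccination". For solicited events, SAP 5.6.1.2 plans tables of worst grade, Grade 3 or higher, time to onset and duration, organised by class and preferred term.

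SAP 5.6.1.3 works in two steps. Step 1 allocates events to periods and names solicited events: "Solicited events are allocated to the phases as described below, however they are always allocated to the respective Post-dose period". Step 2 defines which events are candidates for combination: "Overlapping/consecutive events are defined as events of the same participant with the same preferred term which have at least 1 day overlap". It adds events that begin one day after the previous one ends. Rule 2 then states: "In case overlapping/consecutive events start within a single period, they are considered as one and the same AE". On the records behind a combined event the SAP says: "The individual events which contribute to this AE are retained as individual records in the ADaM database". In the same sentence it says that they "are assigned the same onset, period, and total duration", and it goes on to require related attributes to agree with the combined event. Injection site is not mentioned in Step 2, and solicited events are not exempted.

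**The concern.** SAP 5.6 defines the endpoint per site, but the data rule in 5.6.1.3 cannot tell the sites apart. Solicited local terms are pain/tenderness, erythema and swelling. A reaction in the right arm and one in the left therefore share a preferred term, and after Day 1 both start in the Post-dose 1 period. Rule 2 applies to them whenever their dates overlap or follow directly.

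What is at stake is the timing of local reactions at the ExPEC9V site. The protocol treats timing as informative for this vaccine family. In section 2.3.1 it reports for the predecessor ExPEC10V, in most participants: "Injection site erythema and swelling occurred as late onset events (time to first onset >5 days after vaccination". The safety objective is to describe ExPEC9V given separately or concomitantly. In the CoAd group an ExPEC9V-site event can be merged with an influenza-site event. In the Control group ExPEC9V is the only injection on Day 30, and rule 4 keeps events starting in successive post-dose periods apart, so no cross-site merge is possible there.

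**Working it through.** The plan gives no figure on event merging, so there is none to reproduce. The check applies the rule as written and then illustrates its possible size.

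**Rule as arithmetic.** Let the influenza-site event run from day sF to eF and the ExPEC9V-site event from sE to eE, with the vaccination day as Day 1 (SAP 5.6.1.2 counts onset this way). Duration is counted here as end minus start plus 1. With the same preferred term and known dates (Step 2 treats an imputed end date as known), the events merge if

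max(sF, sE) − min(eF, eE) ≤ 1.

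Both records then carry onset min(sF, sE) and duration max(eF, eE) − min(sF, sE) + 1. Onset can only stay or move earlier, and duration can only stay or lengthen.

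| Influenza site | ExPEC9V site | As written, both records | With a site key, ExPEC9V record |
|---|---|---|---|
| Days 1-3 | Days 2-5 | onset 1, duration 5 | onset 2, duration 4 |
| Days 1-5 | Days 6-9 | onset 1, duration 9 | onset 6, duration 4 |
| Days 2-6 | Days 7-10 | onset 2, duration 10 − 2 + 1 = 9 | onset 7, duration 4 |
| Days 2-4 | Days 7-10 | no merge (7 − 4 = 3) | onset 7, duration 4 |

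In the third row the ExPEC9V-site reaction starts 6 days after vaccination, which is late by the protocol's cut of more than 5 days. After the merge it is recorded as starting 1 day after vaccination.

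**What does not change.** A participant has at least one local event at any site before merging exactly when this is so after it. The worst grade is the maximum over the same records. Neither quantity depends on the merge.

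**Which contrasts are affected.**
- CoAd Day 1 against Control Day 1: both groups have two sites, so the rule acts in both, to different degrees.
- ExPEC9V on Day 1 (CoAd) against ExPEC9V on Day 30 (Control): a cross-site merge is possible only on the first side.

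**Illustration for pain, on assumed inputs.** Only the influenza-site rate of about 42% comes from the documents (41.3% to 42.6%, Protocol 2.3.1). Assumed:
- ExPEC9V-site rate 30% to 60%;
- mean duration 3 days at the ExPEC9V site and 2.5 days at the influenza site;
- mean onset Day 2 or 3 at the ExPEC9V site and Day 1.5 at the influenza site;
- within-person latent correlation 0 or 0.5.

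Simulated results:
- 33% to 61% of ExPEC9V-site events merge;
- mean recorded ExPEC9V-site duration rises from 3.0 to between 3.4 and 3.7 days;
- mean onset moves earlier by 0.2 to 0.6 day (for example 2.0 to 1.77, or 3.01 to 2.45);
- placebo-site events in Control on Day 1, with an assumed rate of 10% and mean duration of 1.5 days, merge in 39% to 73% of cases.

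**The case against.** The best answer is that no careful programmer would merge across arms. Step 2 is generic text for all adverse events, whereas SAP 5.6 specifically asks for local events per site. The table specifications sit in a separate Data Presentation Specifications document, which may settle the matter. Step 2 also says that overlapping events may or may not be combined, and the individual records are kept.

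Part of this stands. Because records are retained, per-site incidence can still be produced if site is kept as a variable. If the onset table pools the two sites, a participant's first onset is already the earlier of the two, and merging changes nothing there; only duration is exposed. The outputs cannot be seen, so it is not established that any table will be wrong.

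The rest does not remove the point. The choice between combining and not combining is governed by the listed rules, and rule 2 leaves no discretion within one period. The retained records carry the merged onset and duration. The related attributes to be aligned are not defined, so it is unclear whether per-site severity is also affected. That SAP 5.6 shows a per-site intent is the reason Step 2 needs the key: the two sections give different instructions.

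**Conclusion.** The point holds as a gap between SAP 5.6 and SAP 5.6.1.3. Applied as written, Step 2 gives touching Day 1 reactions at the two sites one onset and one duration. This distorts per-site time to onset and duration, and any count of events. The clearest effect is on ExPEC9V co-administered on Day 1 beside ExPEC9V alone on Day 30. It should be corrected, but it touches no primary endpoint or hypothesis, and SAP 5.6 provides no formal group comparison of safety. Its size cannot be derived from the documents, because ExPEC9V-site rates and durations are not given. The shifts of 0.2 to 0.6 day in onset and 0.4 to 0.7 day in duration rest on the assumptions listed.

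Three stronger readings are tempting and not supported:

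- A reader might infer that the reactogenicity comparison as a whole is biased. Any-site incidence and worst grade over both sites do not change.
- A reader might infer that late-onset erythema and swelling will be hidden in the CoAd group. That needs the same reaction at the influenza site in the same participant, at 25 mm or more to be Grade 1, lasting at least until the day before the ExPEC9V-site onset. Protocol 2.3.1 lists only pain as a local influenza-vaccine reaction at 10% or more, and no document gives the joint frequency.
- A reader might multiply pain rates and report the result as the number affected: 0.413 × 0.40 × 466 = 77 to 0.426 × 0.60 × 466 = 119 under independence, with a ceiling of 0.426 × 466 = 199. These are participants with pain at both sites under an assumed ExPEC9V rate of 40% to 60%. They are not merged events, and they say nothing about late erythema or swelling.

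**What to change.** In SAP 5.6.1.3, Step 2, state that solicited local events are combined only when participant, preferred term and injection site all match. Define site by the injection given (influenza, or ExPEC9V/placebo) rather than by left or right alone, since Protocol 6.1 allows both injections in one deltoid when medically indicated. In SAP 5.6.1.2, state that Day 1 onset, duration and severity of local events are derived per site before any participant-level any-site summary.

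The cost is a sentence or two in the SAP and one more key variable in the adverse-event dataset program. No new data should be needed, on the assumption that the solicited-event records carry the injection site, as the endpoint in SAP 5.6 implies.

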5.6.1.4. Missing Data

Missing data will not be imputed. Participants who do not report an event will be considered as participants without an event. An AE with a missing severity or relationship will be considered as an AE reported but will be considered as not reported for the severity or relationship. For example, an AE with missing severity will be considered as an AE reported for the analysis of any grade but will be considered as not reported for the analysis of at least Grade 3.

5.6.2. Vital Signs

Vital signs (systolic and diastolic blood pressure [while sitting], heart rate, respiratory rate, and body temperature) will be measured both before vaccination and after the end of the 30-minute observation period. At non-vaccination visits, vital signs may be measured if deemed necessary by the investigator.

Baseline and emerging vital signs abnormalities after vaccination will be listed based on the abnormality gradings in [Appendix 4](#) (Section 6.4). An abnormality will be considered as emerging in a particular period if it is worse than the baseline value. If the baseline is missing, the abnormality is always considered emerging.

Any clinically significant changes in vital signs will be reported as an AE. Any clinically significant changes in vital signs that are observed prior to the first vaccination will be reported as medical history.

5.6.3. Physical Examinations

A full physical examination will be carried out at screening. At all other visits, a targeted (abbreviated and symptom-directed) examination will be performed at the discretion of the investigator, based on clinically relevant issues, clinically relevant symptoms and medical history.

Physical examination findings, including body weight, height, and BMI, will be summarized at baseline using descriptive statistics.

Any clinically significant abnormal findings are recorded as AE and will be analyzed as such.

5.7. Other Analyses

5.7.1. Definition of Subgroups

Immunogenicity is evaluated in the following subgroups.

- Age: ≥ 65 to < 75 years and ≥ 75 years
- UTI: whether reported a history of UTI at enrolment (Yes/No)

5.8. Interim Analyses

No formal interim analysis is planned for this study.

The primary analysis will take place when all participants have performed their Day 59 visit or are discontinued earlier. The primary analysis will include all available safety data and immunogenicity results up to Day 59. The analysis will be performed based on sponsor unblinded data.

The final analysis will include MAAE and SAE data up to the end of the study and will be performed on unblinded data.

5.9. Independent Data Monitoring Committee

An IDMC, will be established as noted in Committees Structure in the CSP Section 10.2, Appendix 2: Regulatory, Ethical, and Study Oversight Considerations. All IDMC members will be external and independent of the sponsor, including at least one medical expert in the relevant therapeutic area and at least one statistician. Safety issues that arise from this study will be reviewed by an IDMC on an ad hoc basis, including all related SAEs and all fatal cases. The IDMC responsibilities, authorities, and procedures will be provided in its charter.

6. SUPPORTING DOCUMENTATION

6.1. Appendix 1: Demographics and Baseline Characteristics

The following demographic and baseline characteristics will be summarized.

Table 7 presents a list of the demographic variables that will be summarized by study intervention and overall for the FAS.

Table 7: Demographic Variables

Continuous Variables:	Summary Type
Age (years)	Descriptive statistics (N, mean, standard deviation], median and range [minimum and maximum]).
Weight (kg)	
Height (cm)	
BMI (kg/m ²)	
Categorical Variables	
Age (≥65 to <75 years, ≥75 years)	Frequency distribution with the number and percentage of participants in each category.
Sex (male, female, undifferentiated)	
Race ^a (American Indian or Alaska Native, Asian, Black or African American, Native Hawaiian or another Pacific Islander, White, Multiple)	
Ethnicity (Hispanic or Latino, not Hispanic or Latino)	
BMI ([underweight <18.5 kg/m ² , normal 18.5-<25 kg/m ² , overweight 25-<30 kg/m ² , obese ≥30 kg/m ²])	
Reported history of urinary tract infection at baseline (yes/no)	
Reported history of hospitalization in prior 2 years (yes/no)	

^aIf multiple race categories are indicated, the Race is recorded as “Multiple”.

